### **Evaluation of sample size**

The sample size has been assessed on the basis of the following rules and assumptions:

1. Statistical provisions.
  - 1.1 the power of the statistical tests " $P = (1 - \beta)$ " is assumed to be 80% (the probability of correct rejection of the null hypothesis is 0.8);
  - 1.2 the probability of a type I error " $\alpha$ " is allowed to be less than 5% (the probability of the erroneous acceptance of an alternative hypothesis is less than 0.05);
  - 1.3 the statistical criteria used are 2-sided;
  - 1.4 the calculation of the sample size is based on the assumptions about the expected effects, mainly declared in the primary efficacy criterion of the Protocol;
  - 1.5 statistical null and alternative hypotheses are formulated as follows:

$$H_0: m_2 - m_1 \leq 0$$

$$H_1: m_2 - m_1 > 0,$$

where  $m_1$  – time to resolution of all the disease symptoms in the Ergoferon group,  $m_2$  – time to resolution of all the disease symptoms in the Placebo group;

- 1.6 the sample size of the first and second groups for the two-sided criterion is calculated with the formula:

$$N_1 = N_2 = \sigma^2 (z_\alpha + z_\beta)^2 / (m_2 - m_1)^2,$$

where  $N_1$  and  $N_2$  – sample sizes of the Ergoferon and Placebo groups;  $\sigma$  – expected standard deviation of the first and second groups;  $z_\alpha$  and  $z_\beta$  – z-criterion values for  $\alpha$  and  $\beta$ ;  $m_1$  – time to resolution of all the disease symptoms in the Ergoferon group;  $m_2$  – time to resolution of all the disease symptoms in the Placebo group;

- 1.7 the final sample size is calculated with the following formula:

$$N_F = N_{PP} / (1 - K_B),$$

where  $N_F$  – final sample size;  $N_{PP}$  – result of calculations in par. 1.6, i.e. the planned number of patients completing the study in accordance with the Protocol;  $K_B$  – exclusion rate.

## 2. Assumptions about the expected effects of the clinical study.

It is assumed that the difference between the average duration of the disease (before recovery / resolution of the disease) in the Ergoferon group and in the Placebo group will be at least 0.5 days, and the standard deviation in both groups will not exceed 1.3 days.

Based on the above statistical rules and assumptions, the size of each group will account for 108 people (sample for the PP analysis).

Given the possible exclusion of the patients during the screening process, as well as in the study for various reasons, it was decided to increase the sample by 25% ( $K_B=25\%$ ) and include at least 288 patients (144 patients in each group).

### ***Statistical criteria***

All the statistical calculations will be performed using two groups of statistical criteria:

- parametric – to assess continuous and interval random variables;
- non-parametric – for:

---

 The formula has been taken from: O'Brien, R. G. and Muller, K. E. (1993), "Unified Power Analysis for t-Tests through Multivariate Hypotheses," in L. K. Edwards, ed., Applied Analysis of Variance in Behavioral Science, 297–344, Section 8.2.1. New York: Marcel Dekker.

- assessments of equality / inequality in the proportion of patients when compared for different visits,
- analysis of frequencies of the compared features,
- assessment of continuous and interval random variables in case of violation of the normality assumption.

#### *Parametric criteria*

The application of parametric criteria will be accompanied by a check for normality of the compared samples (Kolmogorov-Smirnov test).

The following parametric methods and approaches are supposed to be used:

1. To assess the differences of continuous variables obtained in two different (independent) groups – Student t-test for independent samples.
2. To assess the differences of continuous variables obtained in one group at two different visits – Student t-test for for paired samples.
3. To assess the temporal dynamics of the compared indicators – analysis of variance (ANOVA) or covariance (ANCOVA) in the modification with repeated measures.
4. In case of multiple comparisons between the groups will apply a variety of corrections for multiplicity (Dunnett), (Tukey), (Scheffe), Holm adaptive test, etc.
5. In case of abnormal data distribution, approaches with the Generalized Linear Models and / or Mixed Linear Models will be used.
6. Selection of the type of distribution, clarification of the factor and covariance structures of the model is carried out with fit statistics such as AIC (Akaike information criterion).

To perform the above-mentioned statistical tests and techniques, it is assumed that the following SAS procedures are used:

- UNIVARIATE – check for normality of the compared distributions;
- CORR, MEANS – calculation of descriptive statistics;
- TTEST – Student t-test with all the modifications;
- GLM – analysis of Generalized Linear Models for studying temporal dynamics (ANOVA, ANCOVA);
- GENMOD – analysis of Generalized Linear Models.  
MIXED – analysis of Generalized Linear Models.

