### **Secondary endpoints**

1. Time to normalization of body temperature.
2. Time to alleviation of flu-like nonspecific symptoms.
3. Time to alleviation of respiratory symptoms.
4. Flu-like nonspecific and respiratory symptoms total score (TS) for days 2-6 (according to the patient's diary).
5. ARVI severity (based on the area under the curve of TS for days 2-6, according to the patient's diary).
6. Percentage of patients recovered on day 2, 3, 4, 5, and 6 (according to the patient's diary).

---

 Criteria of alleviation of all ARVI symptoms: body temperature  $\leq 37.5^{\circ}\text{C}$  for 24 hours (without subsequent increase within the observation period) + absence of ARVI symptoms /presence of ARVI symptoms with  $\leq 3$ -point of TS.

 Oral temperature  $\leq 37.5^{\circ}\text{C}$  for 24 hours (without subsequent increase within the observation period).

 Absence of flu-like nonspecific symptoms/presence of one mild flu-like nonspecific symptom.

 Absence of respiratory symptoms/presence of one mild respiratory symptom.

7. Rates of antipyretic use per patient during days 1 to 5 of therapy (according to the patient's diary).
8. Percentage of patients with worsening of illness (ARVI complications, including those requiring antibiotics; hospitalization) for 14 days.

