### **Study design**

Study design: multicenter double-blind placebo-controlled randomized clinical study in parallel groups.

The study will enroll patients of either gender aged from 6 months to 6 years old with clinical manifestations of ARVI within the first day after the onset of the disease. Patients will be included evenly (1:1 ratio) in accordance with the age group: 6 months – 3 years 11 months 29 days; 4 years – 6 years 11 months 29 days. Signed information sheet for parents/adopters (informed consent form) will be obtained from all participants' parents/adopters prior to the screening procedures.

Medical history, thermometry, patient examination by a doctor, assessment of ARVI symptoms severity, and nasopharyngeal swabs will be performed at screening visit (Day 1). If the inclusion criteria are met and exclusion criteria are absent, the patient is included in the study.

Nasopharyngeal swabs will be analyzed by real-time reverse transcription polymerase chain reaction (RT-PCR) to identify the most common respiratory viruses, including (1) Influenza A virus; (2) Influenza B virus; (3) Influenza A (H1N1)pdm; (4) Human metapneumovirus; (5) Human respiratory syncytial virus; (6) Human rhinovirus; (7) Human adenovirus; (8) Human bocavirus; (9) Human parainfluenza virus 1; (10) Human parainfluenza virus 2; (11) Human parainfluenza virus 3; (12) Human parainfluenza virus 4; (13) Human coronavirus OC43; (14) Human coronavirus 229E; (15) Human coronavirus HKU1; (16) Human coronavirus NL63.

Patients are randomized into one of two groups: the 1st group patients will take Ergoferon according to the dosage regimen for 5 days; the 2nd group patients will take Placebo according to the dosage regimen of Ergoferon for 5 days.

Patient's parents/adoptive parents are provided with diaries where daily in the morning and at night they record oral temperature (measured by a digital thermometer provided by Sponsor), symptoms of ARVI (according to the 4-point scale), administered drug and concomitant therapy. Doctors instruct parents/adoptive parents how to fill in diaries; the first scores of ARVI

symptoms severity and oral temperature are made by doctors together with the parents/adoptive parents.

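### Mixed models are tied to a normality check, while the GLM default for change over time names no sphericity handling and no per-protocol rule for missed diary days

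*Combined protocol and SAP*

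**What the plan says.** All references are to the combined protocol and SAP.

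- **Endpoint.** Secondary endpoint 4 is "Flu-like nonspecific and respiratory symptoms total score (TS) for days 2-6", taken from the diary. Under Study design, parents make diary entries twice a day: "daily in the morning and at night they record oral temperature", together with symptom scores.
- **Default method for change over time.** Parametric criteria, item 3: "analysis of variance (ANOVA) or covariance (ANCOVA) in the modification with repeated measures". The SAS list in the same section gives PROC GLM for this purpose. Normality is checked with the Kolmogorov-Smirnov test.
- **When mixed models enter.** Item 5: "In case of abnormal data distribution, approaches with the Generalized Linear Models and / or Mixed Linear Models will be used". The SAS list describes the procedure as "MIXED – analysis of Generalized Linear Models" and gives PROC GLM the same generalized-linear label.
- **Covariance.** Item 6: "clarification of the factor and covariance structures of the model is carried out with fit statistics such as AIC". No structure, sphericity correction or reported test is named.
- **Another non-normal route.** Non-parametric criteria, item 2, offers the Friedman test for the same purpose.
- **Missing data.** Under Statistical Analyses, Samples, LOCF is stated within the Full Analysis Set (FAS) paragraph. The per-protocol (PP) set requires completed visits and no significant deviations. It does not name a complete diary as a condition and gives no rule for missed days.

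**The concern.** The choice between repeated-measures ANOVA and a mixed model should turn on how a child's daily scores are correlated and on whether records are incomplete. The plan makes it turn on normality. A linear mixed model in PROC MIXED assumes normal errors, so moving to it because data are non-normal leaves the reason for moving untouched. The two things it does better than PROC GLM are withheld when data look normal.

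For five daily scores in a resolving illness, two consequences are possible if the total score (TS) follows item 3:

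- **Sphericity.** The unadjusted within-child F assumes it. Neighbouring days are likely to be more alike than distant ones, and the spread is likely to shrink as children recover, so the assumption is doubtful.
- **Missed days.** They are either carried forward (FAS) or left without a stated rule (PP set). PROC GLM with a REPEATED statement keeps only children with all days present.

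At stake are the level of one test on a secondary endpoint, and the precision and possible bias of the TS comparison.

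**Working it through.** **1. The plan's own figure.** Inputs from Evaluation of sample size: difference 0.5 days, SD 1.3 days, two-sided 5%, power 80%. The standard two-sample formula gives n = 2 × 1.3² × (1.960 + 0.842)² / 0.5² = 2 × 53.06 = 106.1, so 107 per group by the normal approximation. The noncentral t gives 108 (power 79.97% at 107, 80.3% at 108). Then 108 / (1 − 0.25) = 144 per group. The stated 108 and 144 are reproduced and serve as the group sizes below. (The formula as printed omits the factor 2; the stated 108 includes it.) The 108 is described as the sample for the PP analysis.

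**2. Trigger against remedy.**

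| Problem | GLM repeated measures | MIXED | GENMOD |
|---|---|---|---|
| Non-normal errors | not addressed | not addressed | addressed by choice of distribution |
| Unequal correlation across days | only through adjusted or multivariate tests | modelled | robust (GEE) standard errors |
| Incomplete child records | child dropped (REPEATED form) | all recorded days used | all recorded days used |

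Item 5 sends the first problem to two remedies, of which only the generalized linear model fits. The other two rows do not depend on normality.

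**3. Group-by-day test under no treatment effect.** Let d be the group difference in four orthonormal within-child contrasts of the five days, and E the pooled residual cross-product matrix. The unadjusted statistic is F = [(n/2) d′d / 4] / [tr(E) / (4(2n − 2))] on 4 and 4(2n − 2) degrees of freedom (4 and 856 at n = 108). Greenhouse-Geisser multiplies both by tr(E)² / (4 tr(E²)). The multivariate test is Hotelling's T². The covariance patterns are assumptions; the documents give none. Rejection rates at nominal 5% from 10,000 runs per setting, for 108 / 144 per group:

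| Assumed pattern | True epsilon | Unadjusted F | Greenhouse-Geisser | Multivariate |
|---|---|---|---|---|
| Compound symmetry, 0.6 | 1.000 | 5.0% / 4.8% | 4.9% / 4.7% | 4.8% / 4.8% |
| AR(1), 0.5 | 0.809 | 6.3% / 6.0% | 5.0% / 4.7% | 5.2% / 4.9% |
| AR(1), 0.7 | 0.689 | 7.3% / 7.3% | 5.3% / 5.1% | 5.3% / 5.1% |
| AR(1), 0.8 | 0.631 | 7.5% / 8.0% | 5.1% / 5.3% | 4.9% / 5.3% |
| AR(1), 0.9 | 0.577 | 7.7% / 8.0% | 4.9% / 5.1% | 4.6% / 5.3% |
| AR(1), 0.7, SD falling from 4 to 1.2 | 0.609 | 7.4% / 7.1% | 4.5% / 4.4% | 5.2% / 4.5% |

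A second set of 8,000 runs per setting (108 per group, AR(1) 0.5-0.85, with and without shrinking SD and rounding at zero) gave 5.8%-8.4% unadjusted and 4.5%-5.1% with Greenhouse-Geisser. The group test averaged over days uses one mean per child, so sphericity plays no part in it.

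**4. Missed days in the PP set.** With an assumed independent probability q that a day's score is missing, the share of children lacking at least one of five days is 1 − (1 − q)⁵, and complete-case deletion multiplies the standard error by 1/√((1 − q)⁵).

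- q = 0.03: 1 − 0.97⁵ = 14.1% lost, 108 to about 93 per arm, SE × 1.079.
- q = 0.05: 1 − 0.95⁵ = 22.6% lost, 108 to about 84 per arm, SE × 1.137.
- Mixed model on all recorded days: SE × 1.001 to 1.008.

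The result depends on what counts as a missing day. With two entries a day, each missing independently with probability 5%, and one entry enough, q = 0.05² = 0.0025 and the loss is 1 − 0.9975⁵ = 1.2%. If both entries are needed, the loss is 1 − 0.95¹⁰ = 40.1%. The plan does not say how the two entries form a daily TS.

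**5. Missed days in the FAS.** LOCF fills them before any model is run, so no child is dropped. When scores are falling, the carried value tends to be higher than the one missed, and the filled value is analysed as if observed. The size of this effect cannot be computed from the documents.

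**The case against.** **No endpoint is assigned to PROC GLM.** A reader might infer that the day 2-6 score is committed to item 3. It is not: no method is named for any endpoint, and item 1, a t-test between two groups, could also serve for TS. This stands, so the consequences are conditional. Item 3 is still the only parametric entry for change over time, and the absence of an assignment is itself a gap.

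**LOCF prevents deletion.** A reader might infer that the main efficacy analysis loses every child with a missed day. The FAS rule contradicts that. Deletion can arise only in the PP set, where the plan is silent rather than committed to deletion, and where diaries are checked at Visits 2 to 4. The 3% and 5% rates are assumptions.

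**The inflation is avoidable and narrow.** A reader might infer that the group-by-day test is inflated, or that the treatment comparison as a whole is. Neither follows. Inflation needs both non-sphericity and the unadjusted F. PROC GLM also prints adjusted and multivariate tests, and the averaged group contrast is untouched. What remains is that the plan does not say which test it will report.

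**Items 5 and 6 already help.** Item 5 also offers generalized linear models, which do address non-normality, so the criticism applies only to its mixed-model half. Item 6 is not conditioned on non-normality, but choosing a covariance structure by AIC is a mixed-model step. It does not repair the GLM route and fixes nothing in advance.

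**Conclusion.** The concern holds in limited form. Tying mixed linear models to non-normality is wrong on the plan's own wording, and that conclusion needs no assumption. The consequences for TS are conditional on its following item 3:

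- about 6-8% rejection at nominal 5% for an unadjusted group-by-day F under assumed AR(1) correlation of 0.5-0.9, and no inflation under compound symmetry, with Greenhouse-Geisser or with the multivariate test;
- in the FAS, reliance on LOCF, with a likely upward carry of scores of unknown size;
- in the PP set, an unstated rule that could cost 14% or 23% of children at an assumed 3% or 5% missing per day, and much less or more depending on how a daily score is formed.

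This is one of eight secondary endpoints. The primary endpoint and the sample size are not affected. It is worth correcting because the replacement is better and uses a procedure already listed.

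**What to change.** 1. **Parametric criteria, item 3.** For TS on days 2-6, specify one PROC MIXED model in both FAS and PP, fitted whatever the normality check shows and on all recorded days. Use fixed effects for group, day and group-by-day, unstructured within-child covariance and Kenward-Roger degrees of freedom. The treatment effect is the group difference averaged over days 2-6 with its 95% CI. State how morning and night entries form a daily score.
2. **Samples, FAS.** State that LOCF does not apply to this analysis; otherwise the two instructions conflict.
3. **Parametric criteria, item 5.** Remove mixed linear models as the remedy for non-normality. Use a GENMOD/GEE model, or a rank test on each child's mean TS, as a pre-specified sensitivity analysis and not as a switch triggered by a test.
4. **SAS list.** Correct the descriptions of GLM (general linear models) and MIXED (linear mixed models).

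The cost is plan wording and a few lines of code. Unstructured covariance over five days has 5 × 6 / 2 = 15 parameters, which 216 or more children can support. The mixed model relies on missed days being unrelated to the unseen scores, given the recorded ones. Other pre-specified covariance structures would also be defensible.

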#### *Non-parametric criteria*

Below, there are the main types of possible comparisons with the respective criteria:

1. To assess the differences of continuous variables obtained in two different (independent) groups – Mann-Whitney U-test.
2. To assess the temporal dynamics of the compared indicators – Friedman test, non-parametric analogue of analysis of variance with repeated measures.
3. For the frequency analysis of 2×2 cross tables –  $\chi^2$ -test (if the compared frequencies are greater than 5) or Fisher exact test (if one of the compared frequencies is less than 5).
4. For the frequency analysis of cross tables with independent strata – Cochran–Mantel–Haenszel test (modification of the  $\chi^2$ -test for multiple comparisons).
5. For the frequency analysis of data on the presence / absence of an event or outcome during repeated measures (cross tables with dependent strata) – survival analysis.

To perform the above-mentioned non-parametric statistical analysis options, it is assumed that the following SAS procedures are used:

- FREQ – Friedman test,  $\chi^2$ -test and / or Fisher exact test; Cochran–Mantel–Haenszel test.
- LIFETEST – survival analysis .
- NPAR1WAY – Mann-Whitney U-test.

### ***Safety parameters***

Adverse events recorded during the study will be grouped into frequency tables by severity, seriousness and relationship with the study drug.

### ***Data presentation***

Descriptive statistics will be provided for each study continuous / interval variable. Numerical data will be presented by mean, standard deviation, min and max values. Comparisons suggesting statistical conclusion will have the relevant confidence intervals. Outliers will be analyzed individually. The data will be grouped by visits. The categorical variables will be presented as frequency tables by visits.
